13.1.8. Follow-up of Adverse Events and Serious Adverse Events

All AEs and SAEs must be followed until resolution (or return to baseline status), or until the condition stabilizes or is otherwise explained, or until the subject dies or is lost to follow-up. The investigator is responsible for ensuring that follow-up includes any supplemental investigations

as may be indicated to elucidate as completely as practical the nature and/or causality of the AE/SAE. This may include additional laboratory tests or investigations, histopathological examinations, or consultation with other health care professionals.

The sponsor may request that the investigator perform or arrange for the conduct of supplemental measurements and/or evaluations. If a subject dies during participation in the study or during a recognized follow-up period, the investigator should provide the sponsor with a copy of any post-mortem findings, including histopathology.

13.2. Recording Adverse Events

13.2.1. Adverse Event Recording

Adverse events spontaneously reported by the subject and/or in response to an open question from the study personnel or revealed by observation will be recorded during the study at the investigational site. Any AE (i.e., a new event or an exacerbation of a pre-existing condition) with an onset date after start of study drug administration up to and including the designated follow-up safety visit should be recorded as an AE on the CRF.

Information about all AEs, including SAEs, that occur after a subject has been enrolled, whether before treatment, during treatment, or within 14 days following the cessation of treatment must be recorded. AEs occurring after a subject has begun study drug are designated as treatment-emergent adverse events (TEAEs) to distinguish these from AEs occurring after enrollment, but before treatment. For the purposes of this trial, AEs occurring during the Single-Blind Placebo Rin-in Period will be recorded, but will not be considered TEAEs.

All AEs must be recorded on the AE CRF regardless of the severity or relationship to study drug. It is important that investigators also report all AEs that result in permanent discontinuation of the study drug being studied, whether serious or non-serious.

Out of range clinical laboratory findings (e.g., clinical chemistry, hematology) or findings on other assessments (e.g., electrocardiogram, X-rays, vital signs) per se are not reported as AEs. However, if the out of range finding is deemed clinically significant or is associated with signs and/or symptoms, the finding must be recorded as an AE (and additionally as an SAE if it meets the criteria of being serious; see [Section 13.1.2](#)), as described above.

The investigator should exercise medical and scientific judgment in deciding whether an out of range clinical laboratory finding or finding on other assessment is clinically significant. Usually, the abnormality should be associated with a clinically evident sign or symptom, or be likely to result in an evident sign or symptom in the near term, in order to be considered clinically significant. A clinically significant laboratory abnormality in the absence of clinical symptoms may jeopardize the subject and may require intervention to prevent immediate consequences. For example, a markedly low serum glucose concentration may not be accompanied by coma or convulsions, yet be of a magnitude to require glucose administration to prevent such sequelae.

For each AE, the investigator will evaluate and report the onset (date and time), resolution (date and time), intensity, causality, action taken, serious outcome (if applicable), and whether or not it caused the subject to discontinue the study.

Pregnancy is not an AE; should a pregnancy occur, it must be recorded on a separate pregnancy form and reported as detailed below.

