Subjects who complete the study through the Week 16 visit will be eligible to enter an optional open-label extension (OLE) study, protocol ADS-AMT-MS303. Subjects who withdraw from the study prior to completion of the Week 16 visit will have an early termination visit that includes safety follow-up and efficacy assessments. Subjects who complete 12 weeks of double-blind treatment and elect not to participate in the OLE study will have a final post-treatment safety and efficacy assessment 2 weeks after their Week 16 visit. The end of study (EOS) is defined as when a subject completes the Week 16 visit (if electing to enter the OLE study) or the safety follow-up visit (if electing not to enter the OLE study).

All study visits and efficacy assessments should be scheduled to occur at approximately the same time of day for each individual subject. To the extent practicable, study visits and efficacy assessments should be scheduled to occur when a subject is not likely to be experiencing acute side effects from a concomitant medication (e.g., flu-like side effects following interferon-beta injection). Efficacy assessments should be conducted in following sequence: MSWS-12; T25FW; TUG; 2MWT. Subjects using an assistive device during the walking assessments at Screening should use the same assistive device for all subsequent walking tests. Each subject's efficacy assessment should be performed by the same clinical rater, if possible.

Adverse events (AEs) and concomitant medications will be recorded beginning with the first dose of study drug during the Single-Blind Placebo Run-In Period and continuing through the last study visit.

Diagnosis and Eligibility Criteria:**Inclusion Criteria:**

1. Signed a current IRB-approved informed consent form
2. Male or female subjects between 18 and 70 years of age, inclusive, at the time of Screening
3. Confirmed diagnosis of MS according to the 2017 McDonald criteria ([Thompson et al., 2017](#))
4. Current medication regimen must be stable for at least 30 days prior to screening, and subject must be willing to continue the same dosing regimen for the duration of study participation
5. Maximum Expanded Disability Status Scale (EDSS) score during screening of 6.5

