8.3. Subject Withdrawal Criteria

Subjects will be advised that they are free to withdraw from the study at any time. Reasons that subjects may be withdrawn from the study include the following:

- Subject discontinued study drug (see Section 8.5) and wishes to withdraw
- Subject consent is withdrawn
- Sponsor decision, after discussion with the investigator

If a subject is withdrawn from the study, all efforts will be made to complete the early termination visit that includes efficacy assessments and safety follow-up. In addition, women of childbearing potential will have a post-study pregnancy test performed at the early termination visit.

All information, including the reason for withdrawal, should be reported on the applicable pages of the case report form (CRF).

For subjects who are lost to follow-up, three documented attempts will be made to contact the subject for follow-up information, including reason for discontinuation and follow-up of AEs.

Subjects who withdraw from the study will not be replaced.

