12.9. Early Termination Visit

- Assess and record concomitant medications
- Assess and record AEs
- Complete physical examination
- Blood sample for central laboratory analysis including hematology, serum chemistry, and eGFR
- Urinalysis
- Vital signs (blood pressure, respiratory rate, heart rate, and temperature)
- Obtain subject weight in kilograms
- Blood sample for serum pregnancy test in females of childbearing potential

- Efficacy assessments
- C-SSRS
- Collect used/unused blister cards and evaluate compliance
- Completion of Early Termination Visit CRF, including reason for early discontinuation. (If early termination is due to AE, then a brief narrative of the AE will be recorded in the allocated section of the Early Termination Visit CRF)

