13. ADVERSE EVENTS, SERIOUS ADVERSE EVENTS, AND ADVERSE EVENTS OF SPECIAL INTEREST

During the study, the investigator or study site personnel will be responsible for querying and recording adverse events (AEs) and serious adverse events (SAEs), as detailed in this section of the protocol. In this study AEs and SAEs will be reported from the time of study drug administration until the last study visit or death, or whichever occurs first.

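### Subjects who leave the study early have no scheduled adverse event contact timed to cover the 14 days after their last dose

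*Combined protocol and SAP*

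**What the plan says.** Protocol Section 13.2.1 gives two limits for recording. AEs with onset after the start of study drug "up to and including the designated follow-up safety visit should be recorded as an AE on the CRF". All AEs, including SAEs, "within 14 days following the cessation of treatment must be recorded". The second limit has no exception for subjects who stop early. The same section accepts spontaneous reports, answers to open questions and observation as sources.

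Section 13 gives a third limit: reporting runs "from the time of study drug administration until the last study visit or death". The synopsis, Section 7.1 and SAP 3.1 also record AEs through the last study visit. Section 14.5 and SAP 10.1 instead run to the EOS visit. Section 7.1 and SAP 3.1 define EOS as the Week 16 visit for OLE entrants and the safety follow-up visit for those who decline.

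Subjects who withdraw before Week 16 "will have an early termination visit that includes safety follow-up and efficacy assessments". Section 8.3 adds: "If a subject is withdrawn from the study, all efforts will be made to complete the early termination visit". Section 12.9 lists the ET procedures, including AE assessment and "Completion of Early Termination Visit CRF, including reason for early discontinuation". Neither section, nor either schedule of events, places the visit relative to last dose.

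The safety follow-up visit at Week 18 is, under Sections 7.1 and 12.10, for subjects who finish 12 weeks of double-blind dosing and do not enter the OLE. Footnote b of Appendix A is worded more loosely, but Week 18 is set two weeks after a Week 16 visit that early terminators do not have.

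**The concern.** The protocol sets a 14-day post-treatment recording rule and, for completers leaving treatment, schedules a visit that fits it. Subjects who leave early are under the same rule with no contact timed to meet it. The ET visit could be held within days of the last dose. After that, nobody is scheduled to ask whether anything new has happened.

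The stake is safety ascertainment in subjects who left early. An event that begins after an early ET visit is captured if the subject volunteers it, or if the site is already following that subject for a known event. Otherwise it may not be. The EOS definition adds a smaller wording gap, because Section 14.5 and SAP 10.1 refer to a visit that has no branch for these subjects.

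**Working it through.** The plan gives no figure to reproduce. The check sets the recording rule against the scheduled contacts and then does simple day counts.

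**Scheduled AE contact after the last dose, by route out of treatment**

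| Route | Next scheduled AE contact | Source |
|---|---|---|
| Completes, enters OLE | Week 16 visit doubles as first OLE visit | 7.1 |
| Completes, declines OLE | Week 18 visit, ±2 days | 7.1, 12.10, Appendix A |
| Stops drug, stays on study | Remaining scheduled visits | 8.5 |
| Leaves the study early | ET visit, timing not set; nothing after | 7.1, 8.3, 12.9, Appendix A |
| Lost to follow-up | Three contact attempts | 8.3 |

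**Completers who decline the OLE.** Week 18 − Week 16 = 2 weeks = 14 days. With the ±2-day window the visit falls 12 to 16 days after Week 16. At the early edge, 14 − 12 = 2 days of the window are uncovered.

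**Early terminators.** Let d be the days from last dose to the ET visit. Days of the 14-day window with no scheduled AE question = max(0, 14 − d). The documents give no d, so these values are assumptions that show the range:

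| d (assumed) | Days without a scheduled AE question |
|---|---|
| 0 | 14 |
| 3 | 11 |
| 7 | 7 |
| 10 | 4 |
| 14 or more | 0 |

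**Other routes to capture during that remainder**

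- Sections 13.1.1 and 13.1.8 require follow-up of AEs to resolution or stabilisation. This concerns events already identified, although such contact may bring new ones to light.
- Section 8.3 provides: "For subjects who are lost to follow-up, three documented attempts will be made to contact the subject for follow-up information". This covers subjects lost to follow-up, not those who attend an ET visit and leave.
- Section 13.3.2 asks the investigator, after discharge, to notify related SAEs that he or she learns of. It schedules no enquiry.

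**Number affected.** This cannot be derived. For scale only, 20% of 540 = 108, or 36 per arm of 180. The 20% is a condition attached to the TUG and 2MWT power statement in Section 14.1. The 108 is therefore neither a forecast nor a bound, and it would include subjects with no ET visit and subjects already under AE follow-up.

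**The case against.** There is a good case that the plan already works.

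- **A cutoff exists.** A reader might infer from the EOS definition that AE collection has no end for early terminators. The documents do not support that. The synopsis, Section 7.1, Section 13 and SAP 3.1 all run to the last study visit, which for these subjects is the ET visit. It is also reasonable to treat the ET visit as their follow-up safety visit. This stands. What remains is that this cutoff can fall before day 14.
- **No table turns on it.** SAP 10.1 defines a treatment-emergent AE by onset or worsening on or after randomization, with no end date. Any recorded event is therefore counted. This stands, and the point concerns which events are found, not how they are classified.
- **Unrelated SAEs are not excluded.** Section 13.3.2 read alone might suggest that only related SAEs matter after the ET visit. Section 13.2.1 covers SAEs within 14 days without regard to relationship, and Section 13.3 requires notification within 24 hours. This stands, but the site must still learn of the event.
- **Not every drug-stopper is affected.** Section 8.5 encourages subjects to stay on study after stopping drug. Those who do keep their visits, and a later withdrawal can put the ET visit well past day 14. This stands and narrows the group.
- **The rule can be followed as written.** Since spontaneous reports count, an early ET visit does not breach Section 13.2.1. This also stands. The point is weaker ascertainment, not a contradiction.
- **Some subjects cannot be reached.** One listed reason for withdrawal is "Subject consent is withdrawn". Those who refuse further contact will stay uncovered under any plan.

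None of this supplies a scheduled AE question between an early ET visit and day 14.

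**Conclusion.** The point holds as a low-cost improvement to safety follow-up. For a subject who leaves the study early, between 0 and 14 days of the mandatory recording window pass without scheduled AE enquiry, depending on an interval the plan does not set. Completers who decline the OLE have a visit close to day 14.

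This assumes that at least some ET visits take place fewer than 14 days after last dose. Nothing in the documents prevents it, but they do not say how often it would happen. The number of subjects and the number of missed events are both unknown. A reader might go further and infer biased safety comparisons between arms. The documents give no early-termination rates or ET timing by arm, so that is not supported. Nothing here bears on the efficacy analyses, sample size or power.

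**What to change.** In Section 12.9 and both schedules of events, add a telephone AE/SAE contact about 14 days after last dose, modelled on the Week 5 and 7 calls in Section 12.4. Give it the same ±2-day tolerance as the Week 18 visit, preferably used as day 14 to 16 so that the whole window is covered. It should apply to each early terminator whose ET visit is earlier than that and who has not withdrawn consent to contact.

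For these subjects, define EOS and the end of AE/SAE collection as that contact, or the ET visit if later. Carry this definition through Sections 7.1, 13, 13.3.2 and 14.5 and SAP 3.1 and 10.1.

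The cost is protocol and SAP wording and one short call per affected subject. Some will decline the call, so part of the gap will remain. Sample size, power, blinding and the planned tables do not change.

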13.2.2. Serious Adverse Event Recording

If an AE is determined to be an SAE, in addition to recording the appropriate information on the AE CRF page, the information will also be recorded on an SAE CRF page. Additionally, the basis for determining an AE to be an SAE will be recorded on the SAE CRF. A brief narrative of the SAE must be provided in the allocated section of the SAE CRF page. Follow-up information regarding the SAE, as it becomes available, will also be recorded on the SAE CRF page(s).

13.2.3. Adverse Event of Special Interest Recording

If an AE is determined to be an AESI, in addition to recording the appropriate information on the AE CRF page, the information will also be recorded on the appropriate AESI CRF page. Specific questions pertaining to the AESI will be answered on the AESI CRF page. A brief narrative of the AESI must be provided in the allocated section of the AESI CRF page. Follow-up information regarding the AESI, as it becomes available, will also be recorded on the AESI CRF page(s).

13.3. Reporting Adverse Events

The sponsor has requirements for reporting SAEs to both the local regulatory authority and other regulatory agencies regarding the safety of a drug under clinical investigation. The sponsor or designee must be notified within 24 hours once the investigator determines that an AE meets the protocol definition of an SAE. The procedures for reporting serious adverse events are as follows:

- Complete the “Serious Adverse Event Report”;
- Contact the pharmacovigilance staff member identified on the SAE Report Form and report the Serious Adverse Event within 24 hours of the investigator’s knowledge of the event;
- For fatal or life-threatening events, also fax copies of hospital case reports, autopsy reports, and other documents when requested and applicable.

The investigator must verify the accuracy of the information recorded on the SAE pages with the corresponding source documents, and complete, sign and date the SAE pages.

The sponsor or designee may request additional information from the investigator to ensure the timely completion of accurate safety reports.

Any fatal or life-threatening events should also be reported immediately by telephone to the sponsor’s designee.

The investigator, or responsible person according to local requirements, must comply with the applicable local regulatory requirements concerning the reporting of SAEs to all applicable regulatory authorities and IRBs. Investigators will also be notified of all unexpected, serious, drug-related events (7/15 Day Safety Reports) that occur during the clinical trial. Each site is responsible for notifying its IRB or IEC of these additional SAEs.

13.3.1. Investigator Reporting Requirements

When an investigative site receives an initial or follow-up notification of an SAE or other safety information (e.g., revised Investigator's Brochure) from the sponsor, the responsible person, according to local requirements, must submit this information to the local IRB and keep a copy in their files.

13.3.2. Post-Study Reporting Responsibility

All SAEs, regardless of cause or relationship, which occur from the time of study drug administration up to and including the safety follow-up visit, must be reported to the sponsor or designee. If the investigator learns at any time after a subject has been discharged from the study of an untoward medical occurrence that would have qualified as an SAE during the study, and such event is reasonably related to previous study drug exposure, the investigator should promptly notify the sponsor or designee.

13.3.3. Pregnancy

A pregnancy is not an AE. If a subject becomes pregnant while enrolled in the study following administration of study drug, the sponsor or designee must be notified within 24 hours of the investigator learning of the pregnancy. Administration of study drug will be discontinued immediately and the subject will be followed through the outcome of the pregnancy. The outcome of all pregnancies (spontaneous miscarriage, elective termination, normal birth or congenital abnormality) must be followed up and documented even if the subject was discontinued from the study. If pregnancy occurs in a female partner of a male subject, they will be asked to be consented to obtain additional information regarding the pregnancy. The investigator will be required to complete a Pregnancy Information Form and fax the information to the sponsor or designee.

14. STATISTICS

14.1. Primary Efficacy Endpoint and Sample Size Determination

The primary efficacy endpoint is the proportion of responders in each treatment group (see definition details below).

Based on the results from the Phase 2 study, responder rates of 24% and 33% were observed at Week 4 for subjects treated with placebo and 274 mg ADS-5102, respectively, in the modified intent-to-treat (MITT) analysis set. In the present study, it is anticipated that the placebo response rate at Week 16 will be no greater than 20% and the response rate among subjects treated with 274 mg or 137 mg ADS-5102 will be at least 33%. Using these estimates, 180 randomized subjects per active treatment group and placebo group will be needed for the test of differences in proportions (Farrington-Manning approach for the Miettinen-Nurminen [MN] test) to have 80% power at the 2-sided 5% significance level to detect this 13% difference favoring ADS-5102. Assuming a 5% dropout rate during the 4-week Single-Blind Placebo Run-In Period, 570 subjects will be enrolled in the study to randomize 540.

For this sample size of 180 randomized subjects per group, power will be at least 80% to detect treatment differences (ADS-5102 versus placebo) of -2.7 seconds and 5.0 meters in the changes from baseline at Week 16 in the TUG test and 2MWT when the standard deviation of the changes from baseline is no greater than 6.0 sec and 14.9 meters, respectively, and the dropout rate is not greater than 20%.

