8.5. Discontinuation of Study Drug

Subjects should discontinue study drug if judged necessary by the investigator or sponsor, and reasons may include any of the following:

- eGFR falls below 60 mL/min/1.73 m², confirmed by repeat testing (see [Section 7.4.1](#))
- Need to take a medication that is excluded or that may interfere with study measurements

- Subjects requiring MS treatment adjustment due to disease exacerbation or progression should be discussed with one of the Medical Monitors
- Intolerable or unacceptable AEs
- Positive pregnancy test

Subjects who discontinue study drug will be encouraged to complete the study. If the subject decides to withdraw from the study, he or she will have an early termination visit that includes efficacy assessments and safety follow-up.

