14.4. Efficacy Analyses

14.4.1. Primary Efficacy Analyses

The primary efficacy endpoint is the proportion of responders in the 274 mg ADS-5102 treatment group relative to the placebo group, where a responder is defined as a subject who has a $\geq 20\%$ increase from Baseline to Week 16 in walking speed measured using the T25FW (average of two measurements 5 minutes apart). This analysis will be done using the ITT analyses set. Subjects who fail to have an increase of at least 20% at Week 16 in the T25FW

(feet/seconds) will be considered non-responders. Subjects who do not have an observation at Week 16 for whatever reason will be considered to have an indeterminate outcome and will also be included in the denominators, effectively counting them as non-responders for the purpose of treatment comparisons. However, tabulations of each response category will be provided. For this endpoint, baseline will be defined as the average walking speed (feet/seconds) from the T25FW at Weeks 0 and 2 (prior to randomization).

The objective of the primary efficacy analysis is to test for superiority of the 274 mg ADS-5102 group compared to the placebo group in terms of the difference (active minus placebo) in the proportion of responders at Week 16 using the ITT analysis set. This test of proportions will be done using the MN test at the 2-sided 5% level. Both the 2-sided p-value and the 95% confidence interval (CI) for the difference will be obtained. Superiority will be concluded if the lower limit of the 95% CI is greater than zero (equivalently 2-sided p-value < 0.05).

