3.2. Study Endpoints

3.2.1. Primary

The primary efficacy endpoint is the proportion of responders in each treatment group, where a responder is defined as a subject who has a $\geq 20\%$ increase from Baseline to Week 16 in walking speed measured using the T25FW (average of two measurements 5 minutes apart), in the Intent-to-Treat (ITT) analyses set. Subjects who do not have a Week 16 assessment will be classified as having an indeterminate outcome and will be included in the denominator (i.e., they will be treated as de-facto non-responders). If a subject has not completed two walking tests, then the result for the one T25FW will be used.

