5.11. Data Imputation

Unless otherwise specified, all available efficacy and safety data will be included in data listings and tabulations. Prior to database lock, critical data that are potentially spurious or erroneous will be examined and queried according to standard data management operation procedures.

For the efficacy analyses of responder rates, a subject with missing data will be defined as a non-responder. For all other endpoints, missing data will be treated as missing and no data imputations will be applied, unless otherwise specified. See [Section 9.2.1](#) for sensitivity analyses concerning the missing data assumptions.

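### Does the 80% power for the primary responder test leave out missing Week 16 results?

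*Combined protocol and SAP*

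**What the plan says.** Protocol section 14.1 names the primary endpoint as the proportion of responders, points forward to its definition, and then gives the planning rates. Placebo is expected to be at most 20% at Week 16, and "the response rate among subjects treated with 274 mg or 137 mg ADS-5102 will be at least 33" percent. From these it concludes that "180 randomized subjects per active treatment group and placebo group will be needed for the test of differences in proportions", with 80% power at the two-sided 5% level. The one loss attached to this calculation comes before randomization: "Assuming a 5% dropout rate during the 4-week Single-Blind Placebo Run-In Period, 570 subjects will be enrolled in the study to randomize 540".

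The next paragraph of the section gives power for the Timed Up and Go (TUG) and the 2-Minute Walk Test (2MWT). Unlike the primary statement, it carries a condition: "and the dropout rate is not greater than 20" percent. The synopsis and SAP section 5.2 repeat both statements.

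The definition is in protocol section 14.4.1. Subjects with no Week 16 observation are "included in the denominators, effectively counting them as non-responders for the purpose of treatment comparisons". SAP section 3.2.1 agrees ("they will be treated as de-facto non-responders"), as does SAP section 5.11 ("a subject with missing data will be defined as a non-responder"). Protocol section 8.5 adds: "Subjects who discontinue study drug will be encouraged to complete the study".

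**The concern.** Two things draw the eye. First, the same section allows for up to 20% dropout when it states power for TUG and 2MWT but gives no such allowance for the primary test. Second, the primary analysis turns every missing Week 16 result into a non-response. If the planning rates describe only subjects who were assessed, missing results pull both observed rates down and shrink the difference between them, and a design that only just reaches 80% has nothing in reserve.

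The 33% adds to the doubt. It equals the Phase 2 rate at Week 4 in the MITT set, and the documents do not say how Phase 2 counted missing results.

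The primary test is the gate to all seven key secondary hypotheses, and a non-significant result would be read against the stated 80%. If true power were nearer 70%, that reading would be too confident.

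**Working it through.** **Inputs.** From protocol section 14.1: p0 = 0.20, p1 = 0.33, n = 180 per arm, two-sided α = 0.05. At a null difference of zero the Farrington-Manning statistic is the pooled z-test.

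**Step 1: reproduce the stated power.**

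Power = Φ{[(p1 − p0) − 1.96·SE0] / SE1}, where SE0 = √[2p̄(1 − p̄)/n], SE1 = √{[p0(1 − p0) + p1(1 − p1)]/n} and p̄ is the mean of the two rates.

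- p̄ = 0.265; SE0 = √(2 × 0.265 × 0.735/180) = 0.04652
- SE1 = √[(0.1600 + 0.2211)/180] = 0.04601
- (0.13 − 1.96 × 0.04652)/0.04601 = 0.844, and Φ(0.844) = 0.8006

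Solving for n gives 180. Exact enumeration with the Miettinen-Nurminen variance gives 80.1%. For enrolment, 540/0.95 = 568.4, which the plan states as 570.

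**Step 2: rates are proportions of all subjects, missing counted as non-response.** Missing results are already inside the 20% and 33%, so power is 80% at any missing rate m. The implied rates among assessed subjects are 0.20/(1 − m) and 0.33/(1 − m).

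**Step 3: rates apply to assessed subjects only.** With equal missingness in both arms and missing scored as non-response, the rates analysed become 0.20(1 − m) and 0.33(1 − m), with n still 180. At m = 0.20, for example, they are 0.160 and 0.264, a difference of 10.4 points. Then SE0 = 0.04308, SE1 = 0.04273, and Φ[(0.104 − 1.96 × 0.04308)/0.04273] = Φ(0.458) = 0.676.

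| Assumed missing | Step 2: power | Step 2: implied assessed rates | Step 3: rates analysed | Step 3: power, approximate (exact) |
|---|---|---|---|---|
| 0% | 80% | 20.0% v 33.0% | 20.0% v 33.0% | 80.1% (80.1%) |
| 5% | 80% | 21.1% v 34.7% | 19.0% v 31.4% | 77.3% (77.3%) |
| 10% | 80% | 22.2% v 36.7% | 18.0% v 29.7% | 74.2% (74.4%) |
| 15% | 80% | 23.5% v 38.8% | 17.0% v 28.1% | 71.0% (71.3%) |
| 20% | 80% | 25.0% v 41.3% | 16.0% v 26.4% | 67.6% (68.0%) |

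The missing rates are illustrations. In the plan, 5% is the run-in loss and 20% is the TUG and 2MWT ceiling; neither is a forecast of missing Week 16 walks.

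**Step 4: which scale does the plan use?** Section 14.1 ties the rates to an endpoint whose definition keeps missing subjects in the denominator. It describes the active rate as that of treated subjects and applies it to randomized subjects. It nowhere describes a rate among assessed subjects. These signs all point to Step 2.

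**Step 5: why only TUG and 2MWT carry a dropout condition.** Both are analysed by MMRM on available data without imputation (SAP section 9.2.1), so dropout removes observations and a condition on it is natural. At 180 × 0.80 = 144 per arm, a two-sample t-test gives 81.0% for 2MWT (5.0 m, SD 14.9 m) and 96.8% for TUG (2.7 s, SD 6.0 s), so the stated minimum of 80% holds. In the responder analysis missing subjects stay in the denominator, so missingness acts through the rate and not through n. The different treatment of the two kinds of endpoint is what the Step 2 reading would produce.

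**The case for a change.** The best case for a change is that no sentence says outright which scale the rates are on. The forward reference in section 14.1 is attached to the endpoint, not to the origin of the 20% and 33%. The 33% is carried unchanged from four weeks of treatment in Phase 2 to twelve weeks here, and how Phase 2 treated missing results is unknown. Even the favourable reading has an unstated consequence: at 20% missing, assessed subjects would need to respond at 25.0% and 41.3%. If loss were heavier on active drug, the unfavourable reading gets worse; an assumed 5% missing on placebo and 10% on active gives 65.8%.

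Part of this stands. The assumption is implicit, and whether 33% is a realistic Week 16 rate is open to debate. But that debate concerns the size of the planning effect, not a fault in the power calculation. Setting the implied assessed rates against the Phase 2 24% and 33% settles nothing, because those may themselves count missing as non-response. The lower power figures need both a denominator the plan never uses here and missing rates borrowed from other contexts. Missing also means no Week 16 result, not stopping drug, and subjects who stop drug are encouraged to stay for assessment.

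**Conclusion.** The concern does not call for a change. The 180 per arm and 80% power are correct for 20% against 33%, and they stand whatever the missingness if those rates count missing Week 16 results as non-response, which is what the endpoint definition implies. The drop to about 77% or 68% depends on reading the rates as those of assessed subjects, on assumed missing rates of 5% or 20%, and on equal missingness in both arms.

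This is a gap in wording that a statistician fills from the endpoint definition. Filling it would not alter enrolment, the test, the decision rule or any result. A reader of a negative trial would not be misled for long either: protocol section 14.4.1 requires each response category to be tabulated, including indeterminate outcomes; SAP section 9.1 gives the 95% confidence interval for the difference; and SAP section 9.1.1 repeats the primary analysis in completers with Week 16 data and in the per-protocol set.
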